## **3 STUDY DESIGN**

This is a prospective, non-blinded, non-randomized, non-interventional study of the Masimo pulse oximeter and sensors in a trauma setting.

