## **5 SUBJECT SELECTION AND WITHDRAWAL**

### **5.1 Number of Subjects**

Up to 600 patients will be enrolled to obtain a minimum of two paired data points on 150 subjects.

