#### **7.5 Data Analysis**

This trial will provide baseline data on the performance of SpHb in a population with expected rapid changes in tHb levels. The primary metric to be measured is SpHb's ability to detect critical drops in a trauma population and present the data in a categorical table; statistical significance will be calculated with chi-squared analysis.

The secondary metrics that will be calculated include:

- 1- “Trend capability,” which will be determined by calculating the regression equation and coefficient of determination of a linear mixed effect regression model. The relative differences between data points will be represented graphically with polar plots [Critchley] and 4 quadrant plots.
- 2- Performance of different devices compared to HiCN values (the gold-standard for measuring hemoglobin concentration in blood), including the variability caused by standard of care laboratory devices.
- 3- Absolute accuracy calculation, which will be done by mean test method error with standard deviation, average root mean squared and graphically through Bland-Altman plots [Bland].

Analysis will be performed on the pooled data set as well as separate analyses on all data with high or low signal confidence respectively.

A total of 150 subjects with at least 2 blood samples will be included in the analysis. As a critical drop would require at least two laboratory data points for reference, the study will be powered in order to be 90% confident of achieving that target knowing that 47% of patients recruited in the previous study had at least two paired data points and that it is expected that 20% of patients will be excluded after enrollment (no data points).

An interim analysis will be performed after 50 cases with at least 2 blood samples per case have been completed. This will allow determination of the final sample size in order to obtain an appropriate definition of critical drop detection. The final sample size may be adjusted as a result of this analysis.

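### Section 7.5 lets the final sample size change after a 50-case interim analysis, then applies an ordinary chi-squared test, with no direction, floor, masking or error control stated

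*Combined protocol and SAP*

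**What the plan says.** All the relevant text but the enrolment figure and the design statement is in section 7.5 of the combined protocol and SAP.

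- Primary test: "statistical significance will be calculated with chi-squared analysis". No alpha, sidedness, null hypothesis or reference rate is given.
- Planned size: "A total of 150 subjects with at least 2 blood samples will be included in the analysis". Section 5.1 adds: "Up to 600 patients will be enrolled to obtain a minimum of two paired data points on 150 subjects".
- The look: "An interim analysis will be performed after 50 cases with at least 2 blood samples per case have been completed".
- Its purpose: "This will allow determination of the final sample size in order to obtain an appropriate definition of critical drop detection".
- Its consequence: "The final sample size may be adjusted as a result of this analysis".

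The plan does not say which quantity drives the adjustment, whether N may fall as well as rise, who sees SpHb against the laboratory values at the look, or whether the 50 cases stay in the final test. Section 3 describes the design: "This is a prospective, non-blinded, non-randomized, non-interventional study of the Masimo pulse oximeter and sensors in a trauma setting". The only masking described is in section 7.3, where the sample key is withheld until the sponsor's analyzer has processed the sample. That does not address the interim analysis.

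**The concern.** The chi-squared P value is the only inference planned for the primary metric. It has its nominal level when N is fixed beforehand, or when N is chosen from information unrelated to the association being tested. If N may depend on the interim association between SpHb drops and laboratory drops, the level is no longer guaranteed: the study could stop early on a chance high, or be extended when the result is borderline. This holds even if the critical-drop definition is locked first. A reader of the final report could not tell whether a P value of, say, 0.04 came from a valid 5% test.

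**Working it through.** **Inputs.** From section 7.5: first stage 50 cases, target 150 evaluable, 47% with at least two paired points in the previous study, 20% expected to be excluded after enrolment, 90% confidence of reaching 150. From section 5.1: at most 600 enrolled. Assumed, because the documents give none: two-sided alpha 0.05 (critical value 1.96). The chi-squared statistic on 1 df is treated as Z².

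**The plan's own figure.** I took the smallest enrolment n with exact binomial P(at least 150 evaluable) ≥ 0.90.
- p = 0.47 − 0.20 = 0.27 gives n = 606, close to 600.
- p = 0.47 × 0.80 = 0.376 gives n = 432.

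So 600 is reproduced only by subtracting the two percentages. As a ceiling it is not contradicted by the second reading. The expected evaluable yield from 600 is 600 × 0.27 = 162, 600 × 0.376 = 225.6 (226), or 600 × 0.47 = 282 with no exclusions. These serve as upper limits for N.

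**Set-up.** With Z1 from the first 50 cases and Z2 from the later ones, independent standard normals under the null, the final statistic is

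Z_N = (√50·Z1 + √(N − 50)·Z2) / √N.

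Given Z1 = z, the chance of crossing the upper critical value is 1 − Φ[(1.96√N − z√50) / √(N − 50)]; the lower tail is analogous.

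**Why the choice of N matters.** Take z = 1.8 under the null.
- N = 150: (24.00 − 12.73)/10 = 1.13, rejection probability 0.130.
- N = 60: (15.18 − 12.73)/3.16 = 0.78, rejection probability 0.219.

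Choosing N after seeing z changes the error rate.

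**A simple rule: stop at 50 if significant, otherwise go to 150.** The correlation between the two statistics is √(50/150) = 0.577. The bivariate normal gives 0.05 + 0.05 − P(both significant) = 0.10 − 0.0117 = 0.088.

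**Worst case.** For each z, choose the allowed N that maximises the two-sided rejection probability, then integrate over z.

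| Allowed final N | Maximum false-positive rate |
|---|---|
| 50–150 | 9.5% |
| 50–226 | 10.0% |
| 50–282 | 10.2% |
| 100–226 | 6.3% |
| 150–162 | 5.1% |
| 150–226 | 5.6% |
| 150–282 | 5.8% |

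**Less extreme rules, by simulation.**
- N chosen independently of Z1: 0.0498.
- Conditional-power rule (target 90%), increase only, 150 to 225: 0.049.
- The same rule with decreases allowed to 60: 0.065.

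**Does a combination test repair it?** Weights fixed in advance at √(50/150) and √(100/150) give 0.0496, provided the critical-drop definition is locked. If the definition is picked on the same 50 cases, they do not. With four candidate cut-offs (assumed drop prevalence 10–40%) and N fixed at 150, the weighted test rejected a true null in 7.3% of simulations (largest positive association picked) to 9.7% (largest absolute association picked). Testing only the later cases gave 4.9%.

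**The case against.** The strongest reply is that the plan contains no success test and no early-stopping rule. The look has a stated purpose, and 150 is the number that enrolment is built to deliver, so stopping near 50 is a strained reading. This largely stands as an argument about size: with 150 as a floor, the worst case is 5.6–5.8%, and an ordinary increase-only rule produced no inflation. It does not remove the gap. In section 5.1 the word for a minimum attaches to the paired data points per subject, not to the 150, and section 7.5 then permits adjustment without a direction.

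A reader might infer that the interim look is unmasked. The documents do not say so. Non-blinded describes a single-group, non-interventional design and does not settle who sees an SpHb-by-laboratory table at the look. Linking the look to the definition of drop detection makes such a table plausible, no more.

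It can also be said that the study supplies baseline data, and that a null of no association is barely plausible for a device already cleared to monitor hemoglobin. That lowers the practical weight. But section 7.5 attaches statistical significance to the primary metric, so the claim should be valid or be dropped.

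**Conclusion.** The concern holds as a gap in specification. Followed as written, section 7.5 can yield an invalid P value, and nothing in the plan shows whether it will. At an assumed two-sided 5%, the false-positive rate runs from about 5% (N set without the SpHb result), through at most 5.6–5.8% (increase only from 150, to 226–282 evaluable), to about 9–10% (free choice of N, including stopping at or near 50 on a favourable result).

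A reader might conclude that the plan doubles its error rate. The documents do not support that: doubling needs both use of the SpHb result and freedom to stop at or close to 50, and the plan states neither. The figures also rest on the assumed alpha and on the normal approximation to the chi-squared test, which would be rough if drops are few at 50 cases. They do not include inflation from choosing the critical-drop definition at the same look. That is a further route, and the documents do not allow its size to be fixed.

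**What to change.** In section 7.5:

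1. State alpha and sidedness for the primary chi-squared test.
2. Make 150 evaluable subjects a floor, so that the interim can only raise N, within the existing ceiling of 600 enrolled.
3. Base the new N on the pairing yield and the number of laboratory-defined drops, without tabulating them against SpHb.
4. Lock the critical-drop definition before the look.
5. If SpHb must be examined at the look to choose the definition, keep those 50 cases out of the confirmatory chi-squared test. If the definition is already locked but SpHb results are seen, use a combination test with weights fixed in advance, for example √(50/150) and √(100/150).

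The cost is a few sentences and the option to shrink the study. Item 3 also gives up using the look to tune the definition, which is why item 5 offers an alternative. Excluding the first 50 cases leaves 100 of 150, so standard errors grow by √(150/100) = 1.22. Replacing those cases means 200 evaluable in all, or about 200/0.376 = 532 enrolled on the multiplicative yield, which is within the ceiling. On the subtractive yield it is 200/0.27 = 741, which is not.

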## **8 SAFETY AND ADVERSE EVENTS**

### **8.1 Definitions**

The definitions for adverse event, adverse device effect, serious adverse event, serious adverse device effect, and unanticipated adverse device effect are provided below (ISO 14155:2011, 21 CFR 812.3(s)).

- Adverse Event (AE): an adverse event is any untoward medical occurrence in a subject which need not be related to the device under investigation.
- Adverse Device Effect (ADE): an adverse device effect is any untoward or unintended response to a medical device which may result from insufficiencies in the instructions for use or deployment of the device, or from use error.
- Serious Adverse Event (SAE): a serious adverse event is an adverse event that results in death, inpatient hospitalization, severe or permanent disability, a life threatening illness or injury, fetal distress, fetal death, a congenital abnormality, a birth defect, or medical or surgical intervention to prevent permanent impairment to body or structure.
- Serious Adverse Device Effect (SADE): a serious adverse device effect is an adverse device effect that results in death, inpatient hospitalization, severe or permanent disability or is life threatening.
- Unanticipated Adverse Device Effect (UADE): any serious adverse effect on health or safety or any life threatening problem or death cause by or associated with, a device, if the effect, problem, or death was not previously identified in nature, severity or degree of incidence in the investigational plan, or application (including a supplementary plan or application) or any other unanticipated serious problem associated with a device that related to the rights, safety or welfare of subjects. Refer to the Device Risk Analysis and Risk Assessment section for details on anticipated adverse device effects.

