### **5.2 Inclusion Criteria**

- Estimated 16 years of age or older or greater than or equal to 50 kg body weight if age unknown. (Adult trauma population includes patients 16 years of age and over at MHH).
- Level 1 (highest trauma activation) status at time of arrival to emergency department (ED).
- Expected to be admitted to the ICU/IMU for in hospital care.

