### **8.2 Anticipated Adverse Events:**

The risk from the device is minimal since it is non-invasive and uses wavelengths in the red and near infrared range like a conventional pulse oximeter used in routine clinical practice for over 15 years but can include skin irritation and thermal skin burn from the optical sensors.

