### **8.3 Adverse Event Reporting:**

- All Adverse Events, both Anticipated and Unanticipated, must be recorded in the CRF and in the Adverse Event Report Form.

- All Adverse Events must be promptly reported to the Sponsor.
- All Unanticipated Adverse Device Effects will be also reported to both the Sponsor and the IRB.
- Both Serious Adverse Events and Unanticipated Adverse Device Effects must be reported to the Sponsor within 48 hours. All other Adverse Events should be reported to the Sponsor within 5 business days.
- All Serious Adverse Events will be also reported to the IRB per IRB reporting requirements. These reports may include, but will not be limited to: date of onset; brief description of the events; their treatment; whether they resulted in death, inpatient hospitalization, severe or permanent disability or were life threatening; their relationship to the study device; and resolution.

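### The SADE definition lacks the intervention criterion that the SAE definition has, and neither covers a prolonged hospital stay, so some device harm is misclassified and a narrow group of events escapes 48-hour and IRB reporting

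*Combined protocol and SAP*

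**What the plan says.** Section 8.1 (Definitions) sets out two seriousness lists. For device effects, "a serious adverse device effect is an adverse device effect that results in death, inpatient hospitalization, severe or permanent disability or is life threatening". For adverse events in general, "a serious adverse event is an adverse event that results in death, inpatient hospitalization, severe or permanent disability", followed by threat to life, fetal and congenital outcomes, "or medical or surgical intervention to prevent permanent impairment to body or structure". An adverse event is "any untoward medical occurrence in a subject which need not be related to the device under investigation", so harm from the sensor falls within the adverse event and SAE definitions.

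Section 5.2 (Inclusion Criteria) requires that a subject be "Expected to be admitted to the ICU/IMU for in hospital care". Section 8.2 (Anticipated Adverse Events) describes the device risk as minimal but says it "can include skin irritation and thermal skin burn from the optical sensors". It gives no severity for the burn.

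Section 8.3 (Adverse Event Reporting) has every adverse event recorded in the CRF and on the Adverse Event Report Form. SAEs and UADEs go to the sponsor within 48 hours and also to the IRB. For the rest, "All other Adverse Events should be reported to the Sponsor within 5 business days". Section 8.3 attaches no deadline to SADEs by name. Section 10.5 (Monitoring Plan) has the monitor check the documentation of SAEs and SADEs.

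**The concern.** The two lists ought to use the same threshold for serious, with the SADE list adding only that the device is the cause. They do not, and the protocol gives no reason. The criterion left out of the SADE list is one by which a thermal burn, the more severe of the two anticipated device effects, could become serious without threatening life or causing lasting disability.

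The hospitalization criterion is also a poor fit. It asks whether the event resulted in an inpatient stay, but these subjects are expected to be admitted for their trauma and wear the device for up to the first 24 hours after ED admission (7.2). A device effect in that window will rarely be what causes the admission. What it could do is lengthen the stay, and neither list names that.

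At stake are the classification of device harm and, for a small class of events, how quickly the sponsor hears of it and whether the IRB is told. Section 5.5 waives informed consent and section 1.3 offers subjects no direct benefit, so this classification should be dependable.

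**Working it through.** The check is textual, because the documents state no event rate or safety figure to reproduce. The only arithmetic compares the two reporting windows.

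**Step 1. The lists in 8.1 side by side** (fetal and congenital items omitted; obvious pregnancy is an exclusion under 5.3):

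| Criterion | SAE | SADE |
|---|---|---|
| Death | yes | yes |
| Inpatient hospitalization | yes | yes |
| Severe or permanent disability | yes | yes |
| Life threatening | yes | yes |
| Intervention to prevent permanent impairment | yes | **no** |
| Prolongation of an existing stay | **no** | **no** |

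Every SADE criterion is also an SAE criterion. The reverse fails at the fifth row, and the sixth is missing from both.

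**Step 2. Three sensor burns traced through 8.1 and 8.3:**

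| Burn | SAE? | SADE? | To sponsor | To IRB under 8.3 | Recorded as AE |
|---|---|---|---|---|---|
| (a) Needs intervention to prevent permanent impairment; no other criterion met | yes | no | 48 hours | yes | yes |
| (b) Only serious consequence is a longer stay | no | no | 5 business days, unless a UADE | not required, unless a UADE | yes |
| (c) Death, threat to life, or severe or permanent disability | yes | yes | 48 hours | yes | yes |

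Case (a) loses a label but no time. Case (b) is the only one in which timing and IRB notice change. Case (c) is handled consistently.

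**Step 3. Size of the timing gap in case (b).** With no public holiday, 5 business days span 5 to 7 calendar days, depending on whether a weekend intervenes.

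- Shortest: 5 × 24 h = 120 h; 120 − 48 = 72 h beyond the 48-hour limit.
- Longest: 7 × 24 h = 168 h; 168 − 48 = 120 h beyond it.

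These are differences between deadlines. Section 8.3 also asks for prompt reporting of all adverse events, so actual delays could be shorter.

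**Step 4. Does the UADE route close case (b)?** A UADE must be a serious effect or problem, and an effect on health counts if it "was not previously identified in nature, severity or degree of incidence in the investigational plan". Thermal burn is already identified in nature (8.2), but no severity or incidence is given. Whether a particular burn goes beyond what was identified is therefore a judgement. So is whether a longer stay alone makes it serious, since the UADE definition does not list what serious means. The route may catch case (b), but the text does not ensure it.

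**The case against.** The strongest case on the other side is that this is a wording mismatch with little practical effect. The 48-hour rule depends on SAE and UADE status, not on SADE status, so the SADE omission delays nothing. The SAE report may state the relationship to the device, so device attribution has a place. The study is non-interventional, uses FDA-cleared equipment for up to 24 hours, and has no primary or secondary metric in 7.5 that depends on the SADE label. The documents do not show that serious burns occur at any appreciable rate. All of this stands, and it limits the size of the point.

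It also rules out several stronger readings that a reader might infer:

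- *The definitions cannot grade device harm in inpatients.* They can in part: death, threat to life and disability apply to inpatients in both lists, and the SAE list has the intervention criterion as well.
- *A serious burn goes uncounted.* Section 8.3 records every adverse event; only the SADE classification is affected.
- *A burn needing intervention is reported late.* It is already an SAE.
- *The study could conclude that no SADEs occurred despite serious device harm.* Section 7.5 plans no SADE tabulation or safety conclusion, and 10.5 mentions documentation, not a count.
- *The hospitalization criterion is met by all subjects or by none.* The event itself must result in hospitalization, so admission for trauma does not meet it. A readmission caused by the device would. Section 7.2 also provides for subjects who never reach the ICU/IMU.

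The objection does not remove the mismatch between the lists, or the absence of any prolonged-stay criterion in a population expected to be in hospital already.

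**Conclusion.** The point holds in a limited form and merits a wording amendment. Two gaps remain. First, a device effect that is serious only because it needed intervention to prevent permanent impairment is an SAE but not a SADE; its reporting is unaffected. Second, an event whose only serious consequence is a longer stay is neither. Unless it is judged a UADE, it has a deadline 72 to 120 hours later than the 48-hour limit and needs no IRB report under 8.3. Because adverse events need not be device-related, the second gap also covers complications unrelated to the sensor.

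This rests on reading 8.1 and 8.3 literally and, for the hours, on a week without holidays. The number of events affected cannot be estimated from the documents. Section 8.1 cites ISO 14155:2011 and 21 CFR 812.3(s), but their wording is not reproduced, so conformity with them is not judged here.

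**What to change.** Make two changes in 8.1:

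1. Define SADE as an adverse device effect that meets any SAE criterion.
2. In the SAE definition, replace the hospitalization item with *inpatient hospitalization or prolongation of existing hospitalization*. SADE then takes this over by reference.

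Section 8.3 needs no change. Every SADE would be an SAE, so the 48-hour and IRB rules would apply automatically, and naming SADE there would add nothing.

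The cost is an amendment of wording and a few more events reported within 48 hours and to the IRB. Some of these may be trauma complications unrelated to the device that lengthen the stay without meeting another criterion. No new data item appears to be needed for the second change: hospital and ICU days are already collected (7.4), and subjects admitted to the ICU who have had the first morning laboratory draw are followed for complications through the hospitalization (7.2).

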### **8.2 Anticipated Adverse Events:**

The risk from the device is minimal since it is non-invasive and uses wavelengths in the red and near infrared range like a conventional pulse oximeter used in routine clinical practice for over 15 years but can include skin irritation and thermal skin burn from the optical sensors.

### **8.3 Adverse Event Reporting:**

- All Adverse Events, both Anticipated and Unanticipated, must be recorded in the CRF and in the Adverse Event Report Form.

- All Adverse Events must be promptly reported to the Sponsor.
- All Unanticipated Adverse Device Effects will be also reported to both the Sponsor and the IRB.
- Both Serious Adverse Events and Unanticipated Adverse Device Effects must be reported to the Sponsor within 48 hours. All other Adverse Events should be reported to the Sponsor within 5 business days.
- All Serious Adverse Events will be also reported to the IRB per IRB reporting requirements. These reports may include, but will not be limited to: date of onset; brief description of the events; their treatment; whether they resulted in death, inpatient hospitalization, severe or permanent disability or were life threatening; their relationship to the study device; and resolution.

